4.4 Exploratory Endpoints Analyses

Exploratory endpoints will be performed using the Immunogenicity Analysis Set with available data for the endpoint of interest. Tables will be structured similarly to the primary estimand analysis with Groups 2 and 3 having summaries by baseline Wuhan strain neutralizing antibody titer.

SARS-CoV-2 neutralizing antibody titers against variant strains circulating at the time of analysis (e.g., alpha, beta, delta, and omicron strains) at all available time points will be summarized descriptively using geometric means and 95% CIs for each time point and group.

Total antibody titers measured by ELISA and cellular immune responses measured by ELISPOT will also be summarized using geometric means and their 95% CIs similar to the summaries performed for the neutralizing antibody titers. ELISPOT results will be presented by stimulant pool for Interferon- γ and Interleukin-4.

The geometric means and 95% CIs, as well as fold increases, for both neutralizing antibody titers and total antibody titers will be plotted as a function of time within group, respectively.

Response rates as described in Section 4.2.4 will also be plotted by time point, variant strain, and group.

Pearson's correlation coefficient and 95% CI between the \log_{10} -transformed neutralizing and total antibody titers 2 weeks after the last vaccination will be calculated within group along with the associated p-value. These will also be presented in scatter plots with neutralizing antibodies on the x axis and total antibodies on the y axis.

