8.9 Prohibited Medications

Prohibited medication or medication where washout periods need to be adhered to are (see also eligibility criteria in [Section 1.3](#)):

- Vaccination with any licensed live vaccine within 30 days prior to first or after last trial vaccination or any licensed inactivated vaccine within 14 days prior to first or after last trial vaccination.
- Start of chronic systemic administration (defined as more than 14 days of > 5 mg prednisone [or equivalent]) per day or any other systemic use of immune-modifying drugs during a period starting from 3 months prior to first administration of the trial vaccine and ending at the last visit of the active trial phase. The use of topical, inhaled, ophthalmic and nasal corticoids will be permitted.
- Administration of immunoglobulins and/or any blood products during a period starting from 3 months prior to first administration of the trial vaccine and ending at the last visit of the active trial phase.
- Use of any investigational or non-registered drug or vaccine other than the trial vaccine within 30 days preceding the administration of the trial vaccine, or planned administration of such a drug during the trial period until the FU Visit 3 months after the last vaccination visit for Group 1, or 24 months after last vaccination visit for Groups 2 and 3.
- In case official guidelines require booster vaccinations to maintain valid COVID-19 vaccination certificates, approved booster vaccinations for SARS-CoV-2 are allowed for Groups 2 and 3 within the follow-up period, however subjects will be withdrawn from further follow up.

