
Exploratory
 
 To assess SARS-CoV-2 specific peak humoral immune responses after the prime-boost regimen (Group 1) or the booster dose (Group 2 and Group 3) of the ABNCoV2 vaccine. To explore SARS-CoV-2 specific cellular immune responses to the ABNCoV2 vaccine. To assess SARS-CoV-2 specific neutralizing immune responses against variant strains circulating at the time of analysis. 	
 a) SARS-CoV-2 neutralizing antibody titers at 2 and 4 weeks post-prime vaccination and 1, 4, and 13 weeks post-boost vaccination (Group 1), and 1 week, 4 weeks, 3 months, 6 months, 1 year and 2 years after vaccination (Groups 2 and 3). b) Frequency and percentage of subjects in Groups 2 and 3 with SARS-CoV-2 neutralizing antibody titers having an at least 2-fold increase and 4-fold increase, respectively, from baseline at each sampling time point. c) SARS-CoV-2 total antibody titers (by ELISA) at all sampling time points. Cellular immune response, by Interferon-γ / Interleukin-4 ELISPOT, at 1 week after the last vaccination for all subjects. SARS-CoV-2 neutralizing antibody titers against variant strains circulating at the time of analysis at 2 weeks after last vaccination for all subjects.

Primary Estimand

The primary clinical question of interest is: What peak SARS-CoV-2 neutralizing antibodies titers can be achieved in seronegative (Group 1) and seropositive (Groups 2 and 3) adult subjects after protocol-specified vaccination regimen with ABNCoV2?

Treatment Condition: open-label, non-randomized treatment where subjects follow the protocol requirements and have no deviations from the protocol which would affect their SARS-CoV-2 neutralizing antibody titer levels at two weeks post the last vaccination with ABNCoV2.

Population: Seronegative (Group 1) or seropositive (Groups 2 and 3) adult subjects who meet all of the inclusion and none of the exclusion criteria for the trial, have their 2 weeks post-last vaccination neutralizing antibody titer result, and have no protocol violations which would affect the immunogenicity assessment for the trial.

Endpoint: SARS-CoV-2 neutralizing antibody titer at 2 weeks post-last vaccination (second vaccination for Group 1, and single boost vaccination for Groups 2 and 3).

Intercurrent Events:

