1. Development of COVID-19 symptoms prior to 2 weeks after the last vaccination (Week 6 in Group 1 and Week 2 in Groups 2 and 3) and having a positive test for SARS-CoV-2 infection.

Note, subjects who come in contact with the virus can have significant interference with the SARS-CoV-2 neutralizing antibody levels and thus will be excluded from the primary analysis. This is equivalent to the “while on treatment” strategy.

2. Discontinuation due to AEs from either the second vaccination (Group 1) or the trial (all groups).

Note, for the primary estimand the second intercurrent event is not considered as having an impact on the SARS-CoV-2 neutralizing antibody levels and therefore the “treatment policy” strategy will be used.

Population-level summary:

Group 1 - Geometric mean of SARS-CoV-2 neutralizing antibody titers at 2 weeks after the second vaccination.

Groups 2 and 3 - Geometric mean of the fold increases, defined as the ratio of SARS-CoV-2 neutralizing antibody titer at 2 weeks post single boost vaccination divided by the neutralizing antibody titer at baseline (last measurement prior to ABNCoV2 vaccination).

Rationale for estimand: The primary estimand will allow Bavarian Nordic (BN) in this early phase trial to understand the immunogenic effect of the ABNCoV2 vaccine in subjects treated per protocol specifications to inform future later phase trials.

Secondary Estimands

The secondary clinical questions of interest are:

- What percentage of subjects experience an SAE or AESI assessed as related to trial vaccination within 8 days after vaccination?
- What percentage of subjects experience a Grade 3 or higher AE assessed as related to trial vaccination within 8 days after vaccination?

Treatment Condition: open-label, non-randomized treatment where subjects receive at least one vaccination.

Population: Seronegative (Group 1) or seropositive (Groups 2 and 3) adult subjects who meet all of the inclusion and none of the exclusion criteria for the trial, and have received at least one trial vaccination.

Endpoints: Occurrence of a related SAE, AESI, or Grade 3 or higher AE within 8 days after vaccination.

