2.1 Multiplicity Adjustment

As no formal hypothesis testing will be performed, no adjustments for multiplicity will be needed.

3 Analysis Sets

The target analysis population for the trial includes subjects who meet all of the inclusion and none of the exclusion criteria as defined separately for each group (see Protocol Section 1.3). Subjects in Group 1 will be confirmed to be seronegative, and subjects in Groups 2 and 3 will be confirmed to be seropositive, and be stratified for enrollment by reason for seropositivity such that at least 40 subjects over both groups are enrolled for each of the three reasons for seropositivity (prior COVID-19 infection, prior mRNA vaccination, prior Adenovirus-based vaccination).

For the purposes of analysis, the following analysis sets are defined in [Table 1](#).

Table 1 Analysis Set Definitions

Participant Analysis Set	Description
Safety Analysis Set	All subjects who received at least 1 dose of ABNCoV2 vaccine. Subjects who are vaccinated are included in this set regardless of protocol violations or SARS-CoV-2 infection during the trial.
Immunogenicity Analysis Set	All subjects who are in the Safety Analysis Set and have at least 1 post-vaccination neutralizing antibody titer result. Subjects with protocol violations substantially affecting the immunogenicity outcomes will be excluded from this analysis set. For the purpose of the primary estimand, this includes SARS-CoV-2 infection prior to 2 weeks post last vaccination.

Protocol violations which may exclude a subject from the Immunogenicity Analysis Set may include, but are not limited to:

1. For Group 1, discontinuation prior to receiving both vaccinations
2. Enrollment into the incorrect SARS-CoV-2 exposure group, i.e., a seropositive subject enrolled into Group 1 or a seronegative subject enrolled into Group 2 or 3.
3. Major violation of the visit window affecting the immunogenicity results (i.e., the 2 weeks post-last vaccination serum sample is out of window).
4. Prohibited medication or vaccination given too close to the date of vaccination, or prior to collection of immunogenicity sample for the primary estimand time point, that may affect the immunogenicity results.
5. Major immunogenicity sample handling deviations at critical visits, e.g. regarding clotting time, turnaround time.
6. SARS-CoV-2 symptoms or infection prior to collection of the 2-week post-last vaccination immunogenicity sample.

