4.5.3.4 SARS-CoV-2 Infection Results via PCR

The frequency and percentage of subjects testing positive for COVID-19 infection by visit, any infection prior to 2 weeks post-last vaccination, any infection after the 2 weeks post-last vaccination time point, and any infection post vaccination overall will be summarized by group. As collection may occur during unscheduled visits, frequencies and percentages will include all subjects who tested positive between the prior visit through the summarized visit.

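### The SAP has no rule for titers sampled after a SARS-CoV-2 infection later than the 2-week sample, so its exploratory persistence estimates can mix vaccine response with infection response

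*SAP*

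**What the plan says.** SAP 1.1 states that "subjects who come in contact with the virus can have significant interference with the SARS-CoV-2 neutralizing antibody levels" and removes such subjects from the primary analysis; SAP 4.2.1 repeats the argument.

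The removal has a time limit. In SAP Section 3, Table 1 defines the exclusions from the Immunogenicity Analysis Set and adds: "For the purpose of the primary estimand, this includes SARS-CoV-2 infection prior to 2 weeks post last vaccination". Item 6 of the violations listed below the table uses the same limit: "SARS-CoV-2 symptoms or infection prior to collection of the 2-week post-last vaccination immunogenicity sample". The exclusion list is to be approved before the primary analysis is reported.

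SAP 4.4 then covers the exploratory titers: "Exploratory endpoints will be performed using the Immunogenicity Analysis Set with available data for the endpoint of interest". SAP 4.2.4 adds by-visit summaries, response rates by time point and, for the final report, a response rate that includes the follow-up visits. Under SAP 1.1 the neutralizing titers run to 2 years in Groups 2 and 3 and to 13 weeks post-boost in Group 1.

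Later infections do appear in the plan, but as a safety tabulation: SAP 4.5.3.4 counts "any infection after the 2 weeks post-last vaccination time point". For an approved SARS-CoV-2 booster taken by Group 2 or 3 subjects during follow-up, Protocol 8.9 does set a rule: "however subjects will be withdrawn from further follow up".

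**The concern.** The plan accepts that infection disturbs the measurement and acts on this at 2 weeks. It is silent at the later visits, where there is more time for infection to occur. Neither SAP 4.4 nor Protocol 9.17 names a strategy for infection as an intercurrent event in the exploratory endpoints. An approved booster ends a subject's follow-up; an infection, which can also stimulate the same antibodies, does not.

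The later visits are the trial's only data on how long titers last, and SAP 4.4 plots them over time. If some subjects have been infected in between, the curve no longer describes the vaccine alone. A response rate that includes follow-up could also count someone as a responder because of a post-infection sample. Group 3 enrolls after Group 2 is complete (Protocol 4.1), so the same visit falls at different calendar times. Exposure to infection could then differ between the doses that SAP 4.1 wants to be comparable.

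**Working it through.** **1. Does another rule close the gap?** The list of violations in SAP Section 3 is open-ended, so a later infection could in principle be added. But the list removes whole subjects, and it is fixed before the primary report. SAP 4.6 places that report after the end-of-active-phase (EAP) visit of Groups 2 and 3, before most late samples exist. Removing a subject for an infection at month 9 would also discard a valid 2-week value. SAP 4.6 describes the final analysis as an addition to reported results, not a re-analysis. No sample-level rule exists.

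**2. The plan's own precision figure.** SAP Section 6 assumes an SD of 0.5 (log10) before and after the booster, a correlation of 0.3 and n = 90.

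- SD of the difference = √(2 × 0.5² × (1 − 0.3)) = 0.5916.
- Half-width = 1.96 × 0.5916/√90 = 0.122, as stated.
- At a fold increase of 4: 4 × 10^(±0.122) = 3.0 to 5.3, as stated. As a factor, 0.122 log10 is about 1.33.

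**3. Size of the bias.** Let p be the share of subjects at a visit who were infected earlier, and B the fold contrast still present at that visit. The mean log10 titer shifts by p × log10(B), so the GMT and the geometric mean fold increase are multiplied by B^p. Both p and B are assumptions.

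| p | B = 2 | B = 4 | B = 10 |
|---|---|---|---|
| 10% | 1.07 | 1.15 | 1.26 |
| 20% | 1.15 | 1.32 | 1.59 |
| 50% | 1.41 | 2.00 | 3.16 |

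The bias equals the planned half-width when p = 0.122/log10(B): 41% for B = 2, 20% for B = 4, 12% for B = 10.

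**4. Response rates.** Assume a late fold increase of 1.5 without infection, B = 4 and the same SD of 0.5916.

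- P(at least 4-fold), uninfected = 1 − Φ((log10 4 − log10 1.5)/0.5916) = 23.6%.
- For infected subjects the geometric mean fold increase is 1.5 × 4 = 6, and the same formula gives about 61.7%.
- The mixture (1 − p) × 23.6% + p × 61.7% is 27.4% at p = 10%, 31.2% at 20% and 42.6% at 50%.

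**5. Precision after dropping samples** (n = 90, fold increase 4).

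| Dropped | n | Half-width | 95% CI |
|---|---|---|---|
| 10% | 81 | 0.129 | 2.97 to 5.38 |
| 20% | 72 | 0.137 | 2.92 to 5.48 |
| 30% | 63 | 0.146 | 2.86 to 5.60 |
| 50% | 45 | 0.173 | 2.69 to 5.96 |

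**The case against.** The strongest reply has four parts.

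- **The endpoints are exploratory and descriptive.** The stated exploratory humoral objective concerns peak response, no durability estimand is set, and as-observed summaries are a legitimate choice. This stands as a limit on the stakes. Protocol 4.5 nevertheless gives long-term immunogenicity as a purpose of follow-up, and if a treatment-policy summary is intended the SAP does not say so.
- **A reader might infer that the late titers are inflated, by a known and growing amount.** The documents do not support that. They speak of interference without direction, and give no infection rate and no titer rise. The upward direction is an inference. It has some support, since the protocol accepts prior infection as a reason for seropositivity and counts infection plus one dose as a completed regimen. B must also be the contrast left at the visit, which shrinks if the infection response wanes. At week 4, only about two weeks past the limit, few infections can have accrued.
- **Infection is only partly recorded in follow-up.** After the EAP visit only SAEs and AESIs are collected (Protocol 8.12, SAP 4.5.2.2), and PCR is done only on clinical indication. Mild symptomatic infections can be missed as well as silent ones. This stands: dropping documented infections reduces the bias without removing it.
- **Dropping samples may be informative.** If subjects with low titers are infected more often, those who remain have higher titers. This also stands, and it argues against making the reduced table the main display.

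The plan already tabulates PCR positives by visit and group. That shows the known burden, but does not link it to the titers.

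**Conclusion.** The gap is real and is not closed elsewhere in either document. By-visit GMTs, fold increases and response rates after the 2-week sample combine vaccine persistence with whatever titer later infections induce. To the extent that infections occur and raise titers, the estimates are too high as measures of vaccine persistence.

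The size cannot be fixed from the documents. Over the assumed range of p = 10% to 50% and B = 2 to 10, the factor runs from 1.07 to 3.16. It matches the planned half-width at about 20% infected if B = 4.

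A reader might take this to touch the primary result. It does not: the exclusion covers the period before the 2-week sample. Nor does the 2-year horizon apply to Group 1. This is an inexpensive improvement to exploratory outputs.

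**What to change.** In SAP 4.4 and 4.2.4, for visits after the 2-week post-last-vaccination sample:

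- Keep the as-observed summaries. Add beside them a parallel table and plot of GMTs, fold increases and response rates that drops each subject's samples from the first documented SARS-CoV-2 infection onward. Documented means a positive PCR, or COVID-19 recorded as an AE through the EAP visit or as an SAE or AESI afterwards.
- Report at each visit the number dropped for infection and the number withdrawn for a booster.
- State that infections not tested or recorded in follow-up remain in the data, and that dropping samples may be informative. A repeated-measures model on log10 titer, which lets dropped subjects contribute their earlier values under a missing-at-random assumption, is optional.
- Reconcile SAP 1.2, which describes infection testing through the Active Trial Period, with SAP 4.6 and Appendix 3, which extend it through the last follow-up visit.

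The cost is SAP wording and one further set of outputs from data already collected, with fewer subjects and wider intervals at late visits, as shown in the precision table above.

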4.5 Other Safety Analyses

Safety data will be summarized descriptively using the Safety Analysis Set. AE and medical history data will be coded using the Medical Dictionary for Regulatory Activities (MedDRA) version 24.0, and reported using System Organ Classes (SOCs) and Preferred Terms (PTs). Prior and concomitant medications will be coded to World Health Organization (WHO) Drug Dictionary version March 2021, and will be reported by Anatomic-Therapeutic-Chemical (ATC) Class Level 2 and Preferred Name.

4.5.1 Extent of Exposure

Exposure to trial vaccine will be summarized by group, including the number of vaccinations received as well as the number and percentage of subjects returning memory aids for the Safety Analysis Set. All exposure data will be listed.

4.5.2 Adverse Events

AEs are defined as any untoward medical occurrence after a subject has signed informed consent form, and does not necessarily have a causal relationship associated with the administration of the trial vaccine.

An SAE is defined as any untoward medical occurrence that:

- Results in death
- Is life-threatening
- Requires in-patient hospitalization or prolongation of existing hospitalization
- Results in persistent or significant disability or incapacity
- Results in a congenital anomaly or birth defect
- Is an otherwise important medical event

The criteria for an event being serious will be captured in the AE case report form as reported by the investigator.

AESIs are defined per the Safety Platform for Emergency vACCines (SPEAC) Project generated list of AESI for safety monitoring, and will be flagged as such in the AE case report form by the investigator. For analyses, the investigator assessment as recorded on the AE case report form will be used to identify these AESIs.

4.5.2.1 Solicited Adverse Events

Solicited AEs are defined as all symptoms specifically listed in the memory aid provided to the subjects following each vaccination. After vaccination, the subjects are requested to monitor and record local symptoms (i.e., erythema, swelling, induration, pruritus and pain at the injection site) as well as general symptoms (i.e., body temperature increase/pyrexia, headache, chills, myalgia, nausea and fatigue) in the memory aid daily for the day of vaccination and the following 7 days (Days 1 to 8 following vaccination, 8-day period). If symptoms persist at Day 8, daily symptoms and temperatures will be documented each day until resolved. Solicited AEs that meet the criteria for SAEs will be documented in the AE case report form as well as the memory aids.

As Group 1 receives 2 vaccinations, summaries will be presented by vaccination period and for the overall Active Trial Period. For Groups 2 and 3, there will be a single summary for the Active Trial Period.

Solicited Local AEs

Occurrence, intensity, and duration of solicited local AEs during the 8-day period after vaccination will be summarized for each group. Note, solicited local AEs are always assumed to be related to vaccination so no summaries based on causality will be performed.

Injection site erythema, swelling and induration will be measured using a provided ruler and the maximum diameter will be recorded for each day on the memory aid. The intensity for these symptoms will be graded as follows:

Table 3 Solicited Local Event Grading

MedDRA coded Preferred Term	Grade	Intensity
Injection site erythema, swelling, and induration	0	0
	1	< 30 mm
	2	≥ 30 – < 100 mm
	3	≥ 100 mm
Injection site pruritus	0	Absent
	1	Mild
	2	Moderate
	3	Severe
Injection site pain	0	Absent
	1	Painful on touch
	2	Painful when limb is moved
	3	Spontaneously painful/prevents normal activity

Solicited General AEs

Occurrence, relationship, intensity, and duration of solicited general AEs during the 8-day period after each vaccination will be summarized for each group based on the grades defined below:

Table 4 Solicited General Event Grading

MedDRA coded Preferred Term	Grade	Intensity
Body temperature*	0	< 37.5°C (< 99.5°F)
	1	≥ 37.5 – < 38.0°C (≥ 99.5 – < 100.4°F)
	2	≥ 38.0 – < 39.0°C (≥ 100.4 – < 102.2°F)
	3	≥ 39.0 – < 40.0°C (≥ 102.2 – < 104.0°F)
	4	≥ 40.0°C (≥ 104.0°F)
Headache, Myalgia, Nausea, Chills and Fatigue	0	None
	1	Mild: easily tolerated, minimal discomfort and no interference with daily activity
	2	Moderate: Some interference with daily activity
	3	Severe: Prevents daily activity

*Pyrexia is defined as oral temperature $\geq 38.0^{\circ}\text{C}$ ($\geq 100.4^{\circ}\text{F}$).

Causal relationship between solicited general AEs and the vaccine will be assessed by the investigator using the same categories as for unsolicited AEs (see Clinical Trial Protocol Section 8.1.8).

Analysis

Solicited AEs will be summarized by AE term for overall occurrence and by maximum intensity using frequencies and percentages. Note, only solicited events with intensity grades above 0 are considered AEs, however subjects reporting intensity grades of 0 for the collection period will be included in summaries to account for all observed memory aid data. As intensity is still collected daily for ongoing events after day 8 of the memory aid reporting period, the maximum intensity used in summaries will be derived from the entire duration of the event and not just from the 8-day reporting period.

Group 1 summaries will be performed by period (Vaccination Period 1, Vaccination Period 2, and for the overall Active Trial Period). Groups 2 and 3 will be summarized for the Active Trial Period, separately from Group 1.

In addition, duration of solicited events will be summarized only for subjects experiencing the event of interest using n, mean, SD, median, Min, and Max. Although the collection period is 8 days including the day of vaccination, durations may be longer than 8 days if the solicited event is ongoing at Day 8. For subjects in Group 1 who receive two vaccinations, the maximum duration across the two vaccination periods will be reported for the Active Trial Period summary.

Additional summaries of the subset of general AEs determined to be related to vaccination, as well as those considered both related and \geq Grade 3, will also be presented using frequencies and percentages.

The solicited AE information from the memory aid as well as the physician's assessments and durations will be included in subject-level listings.

